11. ADVERSE EVENT REPORTING

11.1. Definitions

11.1.1. Adverse Events

An AE is any untoward medical occurrence in a subject administered a pharmaceutical product and which does not necessarily have a causal relationship with this treatment. An AE can therefore be any unfavorable and unintended sign (including a clinically significant abnormal laboratory finding, for example), symptom, or disease temporally associated with the use of an investigational study drug, whether or not considered related to the study drug ([ICH-E2A 1995](#)).

For the purposes of this clinical study, AEs include events which are either new or represent detectable exacerbations of pre-existing conditions.

The term “disease progression” should not be reported as an AE term. As an example, “worsening of underlying disease” or the clinical diagnosis that is associated with disease progression should be reported.

Adverse events may include, but are not limited to:

- Subjective or objective symptoms provided by the subject and/or observed by the investigator or study staff including laboratory abnormalities of clinical significance.
- Any AEs experienced by the subject through the completion of final study procedures.
- AEs not previously observed in the subject that emerge during the protocol-specified AE reporting period, including signs or symptoms associated with the underlying disease that were not present before the AE reporting period
- Complications that occur as a result of protocol-mandated interventions (e.g., invasive procedures such as biopsies).

The following are NOT considered AEs:

- **Pre-existing condition:** A pre-existing condition (documented on the medical history CRF) is not considered an AE unless the severity, frequency, or character of the event worsens during the study period.
- **Pre-planned or elective hospitalization:** A hospitalization planned before signing the ICF is not considered an SAE, but rather a therapeutic intervention. However, if during the pre-planned hospitalization an event occurs, which prolongs the hospitalization or meets any other SAE criteria, the event will be considered an SAE. Surgeries or interventions that were under consideration, but not performed before enrollment in the study, will not be considered serious if they are performed after enrollment in the study for a condition that has not changed from its baseline level. Elective hospitalizations for social reasons, solely for the administration of chemotherapy, or due to long travel distances are also not SAEs.

- **Diagnostic Testing and Procedures:** Testing and procedures should not be reported as AEs or SAEs, but rather the cause for the test or procedure should be reported.

11.1.2. Serious Adverse Events

A serious adverse event (SAE) based on International Conference on Harmonisation (ICH) and EU Guidelines on Pharmacovigilance for Medicinal Products for Human Use is any untoward medical occurrence that at any dose:

- Results in death (i.e., the AE actually causes or leads to death).
- Is life-threatening. Life-threatening is defined as an AE in which the subject was at risk of death at the time of the event. It does not refer to an event which hypothetically might have caused death if it were more severe. If either the investigator or the Sponsor believes that an AE meets the definition of life-threatening, it will be considered life-threatening.
- Requires in-patient hospitalization >24 hours or prolongation of existing hospitalization.
- Results in persistent or significant disability/incapacity (i.e., the AE results in substantial disruption of the subject's ability to conduct normal life functions).
- Is a congenital anomaly/birth defect.
- Is an important medical event that may not result in death, be immediately life-threatening or require hospitalization, but may be considered an SAE when, based upon appropriate medical judgment, the event may jeopardize the subject or subject may require intervention to prevent one of the other outcomes listed in this definition. Examples of such events are intensive treatment in an emergency department or at home for allergic bronchospasm, blood dyscrasias, or convulsion that does not result in hospitalization; or development of drug dependency or drug abuse.

Given that the investigator's perspective may be informed by having actually observed the event, and Pharmacyclics LLC is likely to have broader knowledge of the drug and its effects to inform its evaluation of the significance of the event, if either Pharmacyclics LLC or the investigator believes that the event is serious, the event will be considered serious.

11.1.3. Severity Criteria (Grade 1-5)

Definitions found in the Common Terminology Criteria for Adverse Events version 5.0 ([CTCAE v5.0](#)) will be used for grading the severity (intensity) of AEs. The [CTCAE v5.0](#) displays Grades 1 through 5 with unique clinical descriptions of severity for each referenced AE. Should a subject experience any AE not listed in the [CTCAE v5.0](#), the following grading system should be used to assess severity:

- Grade 1 (Mild AE) – experiences which are usually transient, requiring no special treatment, and not interfering with the subject's daily activities

- Grade 2 (Moderate AE) – experiences which introduce some level of inconvenience or concern to the subject, and which may interfere with daily activities, but are usually ameliorated by simple therapeutic measures
- Grade 3 (Severe AE) – experiences which are unacceptable or intolerable, significantly interrupt the subject's usual daily activity, and require systemic drug therapy or other treatment
- Grade 4 (Life-threatening or disabling AE) – experiences which cause the subject to be in imminent danger of death
- Grade 5 (Death related to AE) – experiences which result in subject death

11.1.4. Causality (Attribution)

The investigator is to assess the causal relation (i.e., whether there is a reasonable possibility that the study drug(s) caused the event) using the following definitions:

Not Related: Another cause of the AE is more plausible; a temporal sequence cannot be established with the onset of the AE and administration of the investigational product; or, a causal relationship is considered biologically implausible.

Unlikely: The current knowledge or information about the AE indicates that a relationship to the investigational product is unlikely.

Possibly Related: There is a clinically plausible time sequence between onset of the AE and administration of the investigational product, but the AE could also be attributed to concurrent or underlying disease, or the use of other drugs or procedures. Possibly related should be used when the investigational product is one of several biologically plausible AE causes.

Related: The AE is clearly related to use of the investigational product.

11.2. Unexpected Adverse Events

An "unexpected" AE is an AE that is not listed in the IB or is not listed at the specificity or severity that has been observed. For example, hepatic necrosis would be "unexpected" (by virtue of greater severity) if the IB referred only to elevated hepatic enzymes or hepatitis. Similarly, cerebral thromboembolism and cerebral vasculitis would be "unexpected" (by virtue of greater specificity) if the IB listed only cerebral vascular accidents. "Unexpected" also refers to AEs that are mentioned in the IB as occurring with a class of drugs or as anticipated from the pharmacological properties of the drug, but are not specifically mentioned as occurring with the study drug under investigation.

11.3. Special Reporting Situations

Special reporting situation on a Sponsor study may require expedited reporting and/or safety evaluation include, but are not limited to:

- Overdose of any study drug
- Suspected abuse/misuse of a study drug
- Inadvertent or accidental exposure to a study drug
- Medication error involving a product (with or without subject exposure to the study drug, e.g., name confusion)

If any special reporting situation meets the criteria of an AE, it should be reported on the Serious Adverse Event Report Form. The Serious Adverse Event Report Form should be sent via email or fax to Pharmacyclics Drug Safety, Pharmacovigilance & Epidemiology (DSP&E) or designee within 24 hours of awareness.

11.4. Documenting and Reporting of Adverse Events and Serious Adverse Events by Investigators

11.4.1. Assessment of Adverse Events

Investigators will assess the occurrence of AEs and SAEs at all subject evaluation time points during the study. All AEs and SAEs whether volunteered by the subject, discovered by study personnel during questioning, detected through physical examination, clinically significant laboratory test, or other means, will be recorded in the subject's medical record and on the AEs CRF and, when applicable, on the Serious Adverse Event Report Form.

Each recorded AE or SAE will be described by its duration (i.e., start and end dates), severity, regulatory seriousness criteria (if applicable), suspected relationship to the investigational product, and any actions taken.

11.4.2. Adverse Event Reporting Period

All AEs whether serious or non-serious, will be documented from the time signed and dated ICF is obtained until 30 days following the last dose of study drug or the start date of a new therapy for cGVHD. SAEs will be reported to the Sponsor Drug Safety via an SAE reporting form and will be recorded in the CRF from the time of ICF signing. Non-serious AEs will be recorded in the source documents from the time of ICF signing and will be recorded in the CRF from the first dose of study drug(s).

SAEs reported after 30 days following the last dose of study drug should also be reported if considered related to study drug. Resolution information after 30 days should be provided.

Progressive disease should NOT be reported as an event term, but instead symptoms/clinical

signs of disease progression may be reported. (See [Section 11.1.1](#))

All AEs, regardless of seriousness, severity, or presumed relationship to study drug, must be recorded using medical terminology in the source document. All records will need to capture the details of the duration and the severity of each episode, the action taken with respect to the study drug, investigator's evaluation of its relationship to the study drug, and the event outcome. Whenever possible, diagnoses should be given when signs and symptoms are due to a common etiology (e.g., cough, runny nose, sneezing, sore throat, and head congestion should be reported as "upper respiratory infection"). Investigators must record in the CRF their opinion concerning the relationship of the AE to study therapy. All measures required for AE management must be recorded in the source document and reported according to Sponsor instructions.

All deaths should be reported with the primary cause of death as the AE term, as death is typically the outcome of the event, not the event itself. Autopsy and postmortem reports must be forwarded to the Sponsor, or designee, as outlined above, if allowed per local regulatory guidelines.

If a death occurs within 30 days after the last dose of study drug, the death must be reported to the Sponsor as a SAE.

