7.1.1.5. Adverse Events

The accepted regulatory definition for an adverse event (AE) is provided in [Section 11.1](#). The occurrence of an AE at the time the ICF is signed until first dose should be recorded under medical history in the eCRF form. All medical occurrences after the first dose with study drug

until 30 days after the last dose of study drug that meet the AE definition below must be recorded as AEs in the CRF.

- Grade 1 adverse events do not need recorded
- Grade 2 unexpected **and** possibly/probably/definitely related
- Grade 3 requiring hospitalization **and** unexpected/expected regardless of relationship
- Grade 3 unexpected without hospitalization **and** possibly/probably/definitely related
- All grades 4 & 5 regardless of unexpected/expected or relationship

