8.2.2. Response Follow-up

Required testing for the response follow-up visits (months 1, 2, 3, 6, 9, 12):

- Medical history
- Physical examination, including vital signs, weight, and Karnofsky performance status
- Laboratory evaluation per institutional guidelines including CBC with differential, glucose, BUN, creatinine, total bilirubin, alkaline phosphatase, LDH, albumin, SGOT(AST), SGPT (ALT), CRP, CK, calcium, and magnesium.
- Biomarkers (correlative lab studies)
- Documentation of concomitant medications
- Completion of institutional GVHD assessment form (see Appendix E)
- Completion of a GVHD patient self-report form (see Appendix F)
- Document cumulative corticosteroid use
- Document any new systemic IST and reason for use

- Document treatment-emergent toxicities and adverse events
- Document any IVIG use
- PFTs (at 3, 6, 9 and 12 month visits only)

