9. SUBJECT COMPLETION AND WITHDRAWAL

9.1. Completion

Patients will be considered to be off study if any new systemic immunosuppressant therapy (including ECP) to treat worsening cGVHD is received. No subsequent adverse or serious adverse event reporting will be done. Further follow up off study will be according to institutional requirements.

Patients will be considered to have completed study follow up at 12 months or 30 days after the last dose of ibrutinib whichever comes last. Further off study follow up will be according to institutional requirements.

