10.2.2. Secondary Endpoints

Secondary efficacy endpoints:

To estimate:

- Chronic GVHD response (CR + PR, both individual organ response and overall response, according to 2014 NIH Response Criteria Working Group Report) – See Appendix G.
- Cumulative steroid exposure (total mg methylprednisolone or equivalent).
- Time to discontinuation of systemic immunosuppression (defined as the date that all systemic IST has been discontinued after resolution of all reversible manifestations of cGVHD. Discontinuation of immunosuppressive medications for the purpose of inducing an anti-tumor response after the development of recurrent or secondary malignancy will not be counted as successful discontinuation of IST).
- Failure-free survival (defined as being alive without the requirement for second-line cGVHD therapy). See section 6.3 for definition of second-line cGVHD therapy.
- Non-relapse and overall mortality

Safety endpoints:

To estimate:

- Incidence of grade ≥ 3 adverse events, possibly or probably related to either ibrutinib and/or rituximab.

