10.4. Efficacy Analysis Methods

This is a phase II trial evaluating the safety and efficacy of ibrutinib and rituximab as primary treatment of cGVHD. Efficacy and safety endpoints will be estimated according to the cumulative incidence and Kaplan-Meier methodology in the presence of competing risks. Outcomes will be compared to historical values based on the Gray's test and log rank test respectively. We plan to enroll 35 patients on this study. Patients will be formally monitored for 12 months to evaluate for outcome and safety endpoints (efficacy/safety visits at the completion of month 1, 2, 3, 6, 9, and 12). All other assessments will be done at the physician's discretion or institutional standards. All patients, responders and treatment failures, will be followed for a period of one year. The primary outcome measure will be the proportion of patients that are alive and off all systemic immunosuppression at 12 months following initiation of treatment. The primary endpoint will be estimated according to the Kaplan-Meier methodology in the presence of competing risks. Outcome will be compared to historical values based on the log rank test. Secondary outcome measures will be cGVHD response, cumulative steroid exposure, time to discontinuation of systemic immunosuppression, requirement for second-line cGVHD therapy, non-relapse and overall mortality, failure-free survival and safety. Secondary survival endpoints will be estimated according to the Kaplan-Meier methodology in the presence of competing risks, and outcomes will be compared to historical values based on the log rank test. Secondary time-to-event endpoints will be estimated according to cumulative incidence methodology, and outcomes will be compared to historical values based on the Gray's test (Gray 1988).

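### AE capture closes 30 days after the last dose in 11.4.2 and 7.1.1.5 but runs to month 12 elsewhere, so non-serious related grade 3–4 events in early stoppers are inconsistently captured

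*Combined protocol and SAP*

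**What the plan says.** One group of sections ties adverse event (AE) capture to the last dose.

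- Section 11.4.2 documents AEs "until 30 days following the last dose of study drug or the start date of a new therapy for cGVHD". The only stated exception after that is "SAEs reported after 30 days following the last dose of study drug should also be reported if considered related to study drug".
- Section 7.1.1.5 sets the same limit for the case report form: events "until 30 days after the last dose of study drug that meet the AE definition below must be recorded as AEs in the CRF". It then lists which events qualify.

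A second group ties it to the calendar.

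- Section 10.4: "Patients will be formally monitored for 12 months to evaluate for outcome and safety endpoints". Section 3.1 says the same and follows responders and treatment failures alike for one year.
- Section 8.2.2 lists, among the tasks at months 1, 2, 3, 6, 9 and 12, "Document treatment-emergent toxicities and adverse events". Appendix A marks the AE row at the same visits. Neither is limited to patients on treatment.
- Section 11.4.1: "Investigators will assess the occurrence of AEs and SAEs at all subject evaluation time points during the study". It sends what is found to the AE form.
- Section 9.1: "Patients will be considered to have completed study follow up at 12 months or 30 days after the last dose of ibrutinib whichever comes last". A patient who stops ibrutinib early therefore remains on study to month 12.

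The safety endpoint in 10.2.2 is the incidence of grade 3 or higher "adverse events, possibly or probably related to either ibrutinib and/or rituximab". It does not depend on seriousness and has no time window. Section 10.4 puts safety endpoints under cumulative incidence and Kaplan-Meier methods.

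**The concern.** Take a patient who stops both drugs at month 3, starts no new cGVHD therapy and attends the month 6, 9 and 12 visits. Section 8.2.2 and Appendix A have staff record AEs at each visit. Section 11.4.2 closed the period at month 4 for everything except related serious events. Both rules are in force, and they give different data for the same patient.

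The endpoint counts related grade 3 or higher events whether or not they are serious. If 11.4.2 is followed, each patient's observation time is set by when treatment stopped, and stopping is linked to how treatment is going. If some staff follow one rule and some the other, observation time is not even known. A cumulative incidence needs a defined end of observation, and section 2.2 also wants safety set against the earlier rituximab-alone experience.

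**Working it through.** The plan states no figure on this point, and the sample size of 35 does not depend on it. The check is of dates, events and patients.

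**1. Days outside the window, counted from ibrutinib.** Inputs: 28-day cycles, 12 in all (3.1); a 30-day tail (11.4.2, 7.1.1.5); month 12 taken as day 365. For a stop at the end of cycle k, the window closes on day 28k + 30, and the uncovered time is max(0, 365 − (28k + 30)).

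| Last cycle | Window closes | Uncovered days | Share of 365 | Later AE visits, nominal dates |
|---|---|---|---|---|
| 3 | 84 + 30 = 114 | 251 | 69% | 6, 9, 12 |
| 6 | 168 + 30 = 198 | 167 | 46% | 9, 12 |
| 9 | 252 + 30 = 282 | 83 | 23% | 12 |
| 12 | 336 + 30 = 366 | 0 | 0% | none |

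A full course is covered; the gap exists only for early stoppers.

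**2. The same, counted from rituximab.** Maintenance doses fall at months 4, 7, 10 and 13 (3.1). At 30.4 days a month, a last dose at month m leaves about 365 − (30.4m + 30) days: 213, 122, 31 and 0 respectively. A patient who stops ibrutinib at the end of cycle 3 but has rituximab to month 13 has 251 uncovered days on the first count and none on the second, taking the window from the final dose. The documents do not settle which count applies. Section 5.1 lists both drugs as study medications, 11.4.2 uses singular and plural forms, the ibrutinib dose-modification sections use the term for ibrutinib, and 9.1 counts from ibrutinib alone.

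**3. Which events fall between the rules.** Related serious events stay reportable after the window. Of the events that 7.1.1.5 lists for recording, those that bear on the endpoint and would drop out are related and non-serious:
- unexpected grade 3 events without hospitalisation;
- grade 3 events with an admission of 24 hours or less, because 11.1.2 makes hospitalisation serious only beyond 24 hours;
- grade 4 events, for instance a laboratory cytopenia. Section 1.2.1.3 names grade 3 or 4 cytopenias as an ibrutinib risk, and Appendix A continues blood counts at months 6, 9 and 12.

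Expected, related grade 3 events without hospitalisation are not on the 7.1.1.5 list at any time, on treatment or off, although the endpoint includes them. Moving the time limit alone would not recover these.

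**4. Which patients.** Those who stop early, start no new systemic cGVHD therapy and stay on study. Sections 6.3 and 9.1 take patients given new systemic therapy for worsening cGVHD off study.

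**5. Effect on the estimate.** As a crude proportion, unrecorded months count as event-free, so the incidence can only be too low. If patients are censored when the window closes, there is no bias when the event rate after stopping equals that of patients still observed. The estimate is too high if the later rate is lower, and too low if it is higher. Section 10.4 points to the second kind of analysis but gives no censoring rule for this endpoint.

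**The case against.** A window tied to the last dose is a legitimate choice. The endpoint has no stated horizon, and 8.2.2 speaks of treatment-emergent toxicities, which could be read as importing the 30-day limit. That reading does not reconcile the text: the term is undefined, the same line goes on to AEs without qualification, and 11.4.1 and Appendix A carry no such limit.

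A reader might infer that late events are lost. The documents do not support that. Related serious events remain reportable, new malignancies are reported through follow-up (11.4.5), major hemorrhage has its own route regardless of seriousness (11.4.6), and staff following 8.2.2 would record the rest. Inconsistent capture is what can be shown.

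A reader might also infer a definite understatement of toxicity in percentage points. The documents give neither a rate of related grade 3 or higher events nor a rate of early stopping, and step 5 shows that even the direction depends on the analysis.

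Two further inferences fail. The three-month rituximab interval says nothing about how long toxicity lasts. The blank AE cells on Day 1 and Day 7 in Appendix A lose nothing, because 7.1.1.5 covers everything from the first dose and 11.4.1 requires start and end dates, so the Month 1 visit can pick those events up.

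Within section 11 the plural forms favour counting both drugs. That makes the ibrutinib-only reading less likely, but 9.1 leaves it open.

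**Conclusion.** The conflict stands for a limited group: patients who stop treatment early, start no new cGVHD therapy and remain on study. For them, non-serious related grade 3–4 events after the window are inconsistently captured, and observation time for the related grade 3 or higher endpoint depends on when treatment stopped. Counted from ibrutinib, the disputed time is 83 to 251 of 365 days for stops between the ends of cycles 9 and 3, and zero for a full course. If rituximab counts as study drug, it can be shorter. These figures assume month 12 is day 365 and that 11.4.2 is applied as written. No bias figure can be given from the documents. The primary endpoint and sample size are untouched. The point merits an amendment because the wording is easily aligned and this is the only safety endpoint listed in 10.2.2.

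**What to change.** 1. In 11.4.2 and 7.1.1.5, end AE capture for every treated patient still on study at the later of the Month 12 visit and 30 days after the last dose of either study drug. This follows the later-of form already used in 9.1. Define the last dose for both drugs, and bring the ibrutinib-only count in 9.1 into line.
2. After day 30 post-dose, capture may be limited to related grade 3 or higher AEs and SAEs.
3. Align the 7.1.1.5 list so that all related grade 3 or higher events are recorded on and off treatment. Otherwise the list still omits events that the endpoint counts.
4. In 10.2.2 and 10.4, state that the endpoint is a 12-month cumulative incidence, and whether patients who leave the study are censored or treated as having a competing event.

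Cost: amendment wording, plus some extra late events to grade and attribute. To month 12 this uses visits already scheduled, with no new tests. For a patient given rituximab at month 13, capture would run to about day 425 (13 × 30.4 + 30), past the last visit in Appendix A. That is already so under 11.4.2 if rituximab counts as study drug, and events after month 12 would not enter the 12-month endpoint.
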